5.13. Efficacy Analysis

All efficacy analyses will be performed separately for each FXa inhibitor (i.e., apixaban, rivaroxaban, edoxaban and enoxaparin). In certain cases, a pooled analysis will be provided as well, and is indicated below where appropriate.

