5.14. Secondary Efficacy Analysis

The secondary objective of the study is to assess the relationship between the change from baseline in anti-fXa activity and achievement of hemostatic efficacy in patients receiving an FXa inhibitor who have acute major bleeding and reduced FXa activity.

Analysis

A logistic regression model predicting the log-odds ratio of success of hemostatic efficacy (rated as "Excellent" or "Good"), with the anti-fXa level activity as a covariate will be used to determine the relationship between anti-fXa level and the clinical outcome.

A subset analysis on the Intracranial patients will be performed using a logistic regression with 2 additional covariates: the log of (the baseline ICH volume + 1), and an indicator variable for baseline Infratentorial involvement.

Anti-fXa Level Measurement

Hemostatic efficacy is achieved when the body has time to produce thrombin and a subsequent clot, thus the anti-fXa level during the first few hours after administration is more important than the decrease in anti-fXa level to predict the log-odds of success of hemostatic efficacy. Therefore, the on-treatment nadir value will be used in the analysis.

Standardization Across Inhibitors

The most power would be gained if it were possible to pool the data across all the anti-fXa inhibitors, however, anti-factor Xa activity levels cannot be combined in the same analysis due to the different bioavailability and pharmacokinetics of the individual FXa inhibitors, especially between the direct and indirect FXa inhibitors. An alternative way to use the activity level that would enable pooling the data is to convert the continuous measurements into a dichotomous variable indicating a level that has similar anticoagulant effects across the 4 different inhibitors.

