For the DOACs, current guidelines by the subcommittee on control of anticoagulation of the International Society on Thrombosis and Hemostasis (ISTH) and the French Working group on perioperative hemostasis (GIHP) recommend using a value of 30 ng/mL to determine if antidote administration should be considered.[4, 5] Unfortunately there is no similar threshold for the indirect anticoagulants, therefore the threshold for the Enoxaparin patients in the analysis will be the lower limit of detection (0.10 IU/mL). Sensitivity analyses excluding patients taking Enoxaparin will be performed as well, with (1) the log of anti-fXa at on-treatment Nadir as a covariate, and (2) the dichotomous variable for anti-fXa less than the threshold as a covariate.

A summary of the planned analyses is below:

Model	Population	Reduced Model covariates	Full Model covariates
1	Efficacy, excluding patients with Non-Evaluable Hemostatic Efficacy due to Admin reason	None (intercept only model)	Indicator variable for on- treatment Nadir anti-fXa level < threshold*
2	Same as (1) except exclude Enoxaparin patients also	None (intercept only model)	Indicator variable for on- treatment Nadir anti-fXa level < threshold*
3	Same as (1) except exclude Enoxaparin patients also	None (intercept only model)	Log of on-treatment Nadir anti-fXa level

4	Same as (1) except exclude non-ICH patients also	Log of (baseline ICH volume +1), Indicator	Reduced Model covariates plus Indicator variable for
	non-reri patients also	variable for Infratentorial	on- treatment Nadir anti-
		involvement	fXa level < threshold*

^{*}The threshold=30 ng/mL for Apixaban, Rivaroxaban and Edoxaban, and 0.10 IU/mL for Enoxaparin.

Descriptive statistics, odds ratios with the corresponding 95% confidence intervals, and p-values from the models will be presented. The Full Model will be compared to the Reduced Model with a Likelihood Ratio Test. The Reduced Model will be rejected in favor of the Full Model if the Likelihood Ratio Test p-value is <0.05.

The area under the receiver operating characteristic (AUC under ROC) with the 95% CI will be presented.

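### SAP 5.14 Model 3 fits one slope on log nadir anti-fXa across three direct inhibitors with no inhibitor term, so if nadir and hemostatic success both differ by drug, inhibitor confounds the estimated relationship

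*SAP*

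**What the plan says.** SAP 5.14 examines whether on-treatment anti-fXa activity predicts effective hemostasis. On pooling across drugs it says that "anti-factor Xa activity levels cannot be combined in the same analysis due to the different bioavailability and pharmacokinetics of the individual FXa inhibitors", adding "especially between the direct and indirect FXa inhibitors". Its remedy is to "convert the continuous measurements into a dichotomous variable indicating a level that has similar anticoagulant effects across the 4 different inhibitors": below 30 ng/mL for the direct inhibitors and below 0.10 IU/mL for enoxaparin.

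The table of planned models then lists four logistic regressions. Models 1, 2 and 4 use the threshold indicator. Model 3 does not:

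- Population: "Same as (1) except exclude Enoxaparin patients also", which leaves apixaban, rivaroxaban and edoxaban.
- Reduced model: intercept only.
- Full model: "Log of on-treatment Nadir anti-fXa level", and nothing else.
- Decision: likelihood-ratio test at p < 0.05.

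SAP 5.13 sets the default that "All efficacy analyses will be performed separately for each FXa inhibitor", with pooled results added in certain cases. No by-inhibitor fit is listed for Model 3. SAP 5.4 plans no covariate adjustment. The confounder analyses in SAP 5.15.1.11 do not name the inhibitor, and they are deferred to an addendum and labelled post hoc.

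SAP 5.3, on the other hand, describes the direct inhibitors as similar in structure, pharmacokinetics and function, with activity in ng/mL tracking plasma concentration one to one.

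**The concern.** Two statements in the SAP pull apart. Section 5.14 says the levels of individual inhibitors should not be combined, and singles out direct versus indirect only as the worst case. Section 5.3 says the direct inhibitors are alike. Model 3 is consistent with 5.3 but not with the reason given in 5.14.

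The statistical issue does not depend on which statement is right. Even on a perfectly common ng/mL scale, a single slope over three drugs mixes two things: the relationship between patients on the same drug, and the contrast between drugs. If drugs with higher nadirs also have a different success rate for another reason, the contrast enters the slope. Bleed mix is one such reason, since Protocol Appendix B rates bleed types by different criteria. Andexanet dose is another, since it depends on the inhibitor (Protocol Table 3).

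Model 3 is the only listed model that uses the continuous level, so it is the natural check on the dichotomised models. A false signal there would appear to corroborate them. A true signal could also be hidden.

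**Working it through.** **The plan's own figures.** None is given for Model 3. The one power statement (SAP 3.2: 162 evaluable patients, 61% against 50%, 80%) reproduces. At least 94 responders are needed, the exact one-sided tail at 50% is 0.0246, and power at 61% is 80.5%. The point does not rest on it.

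**Do the documents make differing nadirs plausible?** In Protocol 3.4.4, Phase 2 anti-fXa activity fell by 91–95% with apixaban, leaving 100 − 95 = 5% to 100 − 91 = 9%. With rivaroxaban it fell by 76–81%, leaving 19% to 24%. The ratio of residuals is 19/9 = 2.1 to 24/5 = 4.8. Baseline selection also differs: at least 75 ng/mL for apixaban and rivaroxaban, 40 ng/mL for edoxaban (SAP 5.2.2). Protocol 3.4.2 reports that 80% of edoxaban patients were below 75 ng/mL.

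**Assumptions, not from the documents.** 300 direct-inhibitor patients; apixaban/rivaroxaban/edoxaban mix 55/37/8%; SD of log nadir 1; geometric mean nadirs and success rates as tabulated. There is no relationship within any inhibitor.

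**Hand check of one case** (nadirs 9/20/40 ng/mL, success 85/75/70%).

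- Log nadirs 2.197, 2.996, 3.689; weighted mean 2.612; deviations −0.415, 0.384, 1.077.
- Mean success 0.55 × 0.85 + 0.37 × 0.75 + 0.08 × 0.70 = 0.801; deviations 0.049, −0.051, −0.101.
- Between-drug covariance = 0.55(−0.415)(0.049) + 0.37(0.384)(−0.051) + 0.08(1.077)(−0.101) = −0.0271.
- Between-drug variance of log nadir = 0.242; total = 1 + 0.242 = 1.242.
- Approximate log-odds slope = (−0.0271/1.242)/(0.801 × 0.199) = −0.137, an odds ratio of about 0.87 per log unit where the within-drug value is 1.
- Approximate standard error = 1/√(300 × 1.242 × 0.801 × 0.199) = 0.130, so z is centred at −1.06.
- Rejection probability = Φ(1.06 − 1.96) + Φ(−1.06 − 1.96), about 18%.

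The covariance is zero if either the nadirs or the success rates are equal across drugs, and the test then returns to about 5%.

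**Simulation** (1,500 runs per scenario for Model 3, 2,000 for Model 2; one-degree-of-freedom likelihood-ratio test at 3.841):

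| Nadirs, ng/mL | Success, % | Model 3 as written | Model 3 with inhibitor in both versions | Model 2 as written |
|---|---|---|---|---|
| 9/15/30 | 85/75/70 | 11.8% | 5.1% | 10.2% |
| 9/15/30 | 85/70/70 | 16.2% | 5.5% | 9.5% |
| 9/15/30 | 75/85/85 | 9.7% | 5.3% | 6.8% |
| 9/20/40 | 85/75/70 | 20.3% | 6.4% | 13.0% |
| 9/20/40 | 85/70/70 | 24.7% | 5.3% | 16.5% |
| 9/20/40 | 75/85/85 | 14.5% | 6.3% | 11.8% |
| either set | equal | 5.3–5.5% | 5.2–5.4% | not tabulated |

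Applying the 4 ng/mL floor of SAP 5.5.1 changes little: 19% against 5% for 9/20/40 with 85/75/70%, and 15% against 5% with 75/85/85%. In the latter case the pooled odds ratio is about 1.15, so a higher nadir appears to help.

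**Sensitivity to the assumptions.** A second set used a 50/40/10% mix, log SD 0.8, the floor, and nadirs 10/20/30 ng/mL. N was 162, or 320 (477 × 0.70 × 0.95 = 317, rounded).

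- Success gap between apixaban and the other two of 5, 10 or 20 points: 6.9%, 10.1% and 27.0% at N = 162; 7.5%, 17.9% and 49.3% at N = 320.
- With inhibitor added, every scenario in this set lay between 4.6% and 6.0%.
- At N = 162, equal nadirs with success 85/75/75% gave 4.8%; differing nadirs with equal success gave 5.6%.

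**Masking.** With N = 300, a true within-inhibitor odds ratio of 0.70 per log unit and success 75/85/85%, Model 3 detects the relationship in 18% of trials, against 60% with inhibitor included. With equal success the figures are 48% and 59%.

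**The case against.** The strongest reply has four parts.

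*The scale problem is largely gone from Model 3.* Excluding enoxaparin removes the unit mismatch and the contrast that SAP 5.14 singles out, and SAP 5.3 supports a common scale for the rest. This stands as far as it goes. A reader might infer that Model 3 fails because ng/mL values of different drugs are incommensurable, but the documents conflict on that. The calculations contain no scale mismatch. What they show is ordinary confounding by inhibitor, which is why Model 2, the SAP's own pooling device, shows it too.

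*The inputs are assumed.* This also stands. The Phase 2 figures come from healthy subjects, and Protocol 3.4.3 describes similarly large reductions for the other inhibitors at the planned or lower doses. Lower edoxaban baselines could even reverse the assumed ordering of nadirs. With success of 82/79/78%, rejection is only 5.2% to 6.2%.

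*The stakes are low.* SAP 5.14 presents Model 3 as a sensitivity analysis, and SAP 5.7 treats secondary analyses as exploratory. SAP 5.13.1.2 summarises both primary endpoints by inhibitor, and the sample output lists include hemostasis by inhibitor and percentage reduction (Table 14.2.2.6). Differences between drugs would therefore be visible. Visibility does not correct the slope or its p-value.

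*Conditioning on drug is a choice of estimand.* If one drug is reversed less well and bleeds more for that reason, adjustment removes genuine signal. This stands, and it is the reason to keep the unadjusted fit on display.

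**Conclusion.** The point holds in a conditional form. Model 3 pools continuous nadirs over three drugs with no inhibitor term, against the reasoning of its own section, and no other planned analysis supplies the term. When nadir and success both differ by inhibitor, a nominal 5% test rejects in about 10% to 25% of trials under the main assumptions (up to 49% in the most extreme case examined), and the odds ratio may point either way. When only one differs, error is near 5%.

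A reader might go further and infer that the Model 3 test has lost its 5% error rate outright, or that the study's efficacy conclusions are compromised. The documents support neither. The inflation needs two differences that they do not quantify, and no primary claim depends on this model. Nor does any version of Model 3 estimate a within-patient relationship. Each patient contributes one nadir and one outcome, so the adjusted slope is between patients, within inhibitor.

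This is worth changing because the remedy is small, and Model 3 is the only listed model that uses the continuous level.

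**What to change.** In the model table of SAP 5.14, add FXa inhibitor (apixaban, rivaroxaban, edoxaban) as a class effect to both the Reduced and the Full version of Model 3, so that the likelihood-ratio test concerns the slope between patients within inhibitor. Report inhibitor-adjusted fits beside the other pooled models, including Model 1. Show the slope per inhibitor as a supporting display. Allow stratified or penalised likelihood if edoxaban numbers are small: 8% of 300 would be 24 patients, and unpenalised fits gave convergence warnings in simulation. Reconcile the statements in SAP 5.3 and 5.14 on whether the direct inhibitors are pharmacokinetically comparable.

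The cost is two degrees of freedom in Model 3 and no new data. Any true between-drug part of the relationship will no longer be credited to anti-fXa activity, so keep the unadjusted Model 3 as a supporting display and say what each fit estimates.

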5.5. Handling of Dropouts and Missing Values

5.5.1. Anti-fXa Activity

For patients treated with apixaban, rivaroxaban, and edoxaban, anti-fXa values greater than 950 ng/mL the anti-fXa value will be replaced with 950. If the anti-fXa value is < 4.0 ng/mL then the value will be replaced with 4.0. For enoxaparin treated patients, anti-fXa values identified as < 0.10 IU/mL will be replaced with 0.10.

If the baseline anti-fXa activity is missing, the patient will be excluded from the efficacy analysis population. For post baseline assessments, if both the EOB and EOI assessments are missing, the maximum change will be replaced with zero (i.e., no change from baseline) and the Nadir will be replaced with the baseline value using the Baseline Observation Carried Forward principle (BOCF principle). If only one post-baseline sample is missing, the available sample (either EOB or EOI) will be used for the imputation (Last Observation Carried Forward [LOCF]).

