 the value will be taken as LLOQ threshold value.
- For plasma concentrations that are higher than the upper level of quantification (ULOQ) then the value will be taken as ULOQ threshold value.

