5.16. Safety analysis

All safety analyses will be conducted using the Safety analysis population. Unless otherwise indicated, all analyses will be presented for an overall population (pooled across the different inhibitors) and stratified by the different inhibitors.

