All deaths will be assessed, and the causes of death adjudicated, by the EAC. Deaths due to cardiovascular causes (i.e., resulting from MI, sudden cardiac death, heart failure, stroke, CV procedures, CV hemorrhage, and other CV causes) will be classified as related to bleeding or non-hemorrhagic.

Kaplan-Meier curve for time to death will be presented by treatment by FXa inhibitor, and exanet dose, and and exanet manufacturing process. Patients who discontinue the study prior to Day 30 with an unknown survival assessment will be censored at the time of the last visit. Also, patients that completed the study (i.e., Day 30) will be censored at Day 30.

In addition, the proportion of patients that died during the 30 day follow-up with exact 95% CI will be presented for the overall safety population, by age category, region, FXa inhibitor, bleeding type, and exanet dose, and exanet manufacturing process, and by age deciles. In addition, the cause of death will be summarized.

The relationship between anti-fXa and 30-day mortality, will be analyzed (in the safety population), using a logistic regression model, with Age included as a covariate.

- 30-day mortality will define Death as Death at any time (including deaths recorded after Day 30). A sensitivity analysis defining Death as above (died during the 30 day followup) will be performed as well.
- Age will be entered into the model using a cubic spline transformation to best reflect the relationship with mortality.

- The Full Model will be compared to the Reduced Model with a Likelihood Ratio Test. The Reduced Model will be rejected in favor of the Full Model if the Likelihood Ratio Test p-value is <0.05.
 - Reduced Model: includes Age (with cubic spline transformation)
 - Full Model: includes Age (with cubic spline transformation) and an indicator variable for anti-fXa at on-treatment Nadir < threshold (where the threshold is 30 ng/mL for the DOACs, and 0.10 IU/mL for Enoxaparin).
- The area under the receiver operating characteristic (AUC under ROC) with the 95% CI will be presented for the Full Model.
- Descriptive statistics, odds ratios with the corresponding 95% confidence intervals, and p-values from the models will be presented also.

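### The enoxaparin cut-off equals the floor already applied to the data, so no enoxaparin patient can be coded as below threshold in Model 1, Model 4 or the 30-day mortality model

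*SAP*

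**What the plan says.** **Replacement rules.** SAP 5.5.1: "For enoxaparin treated patients, anti-fXa values identified as < 0.10 IU/mL will be replaced with 0.10". For the three direct inhibitors the floor is 4.0 ng/mL. SAP 5.5.4 works the same way in general: a result recorded as below x is analysed as x. SAP 5.9 has a similar rule for plasma concentrations under the quantification limit ("the value will be taken as LLOQ threshold value").

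**Nadir.** SAP 4.3 takes the smaller of the end-of-bolus and end-of-infusion values. Under 5.5.1, if one is missing the other is used; if both are missing the baseline value is used.

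**Indicator.** SAP 5.14 explains that levels cannot be pooled across inhibitors and proposes instead to "convert the continuous measurements into a dichotomous variable indicating a level that has similar anticoagulant effects across the 4 different inhibitors". The cut-off is 30 ng/mL for the direct inhibitors. Because no comparable figure exists for enoxaparin, "therefore the threshold for the Enoxaparin patients in the analysis will be the lower limit of detection (0.10 IU/mL". The model table defines the covariate as nadir strictly below the threshold. Model 1 includes all four inhibitors, and Model 4 is its ICH subset ("Same as (1) except exclude non-ICH patients also"). For Models 2 and 3, "Sensitivity analyses excluding patients taking Enoxaparin will be performed as well". SAP 5.16.3 (Deaths) adds to the mortality model "an indicator variable for anti-fXa at on-treatment Nadir < threshold (where the threshold is 30 ng/mL for the DOACs, and 0.10 IU/mL for Enoxaparin", in the safety population.

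**By-inhibitor output.** SAP 5.13 asks for efficacy analyses separately by inhibitor. SAP 5.16 says: "Unless otherwise indicated, all analyses will be presented for an overall population (pooled across the different inhibitors) and stratified by the different inhibitors".

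**The concern.** The floor and the cut-off are the same number and the comparison is strict. An enoxaparin patient whose activity becomes undetectable is stored as 0.10, and 0.10 is not below 0.10. Choosing the detection limit as the cut-off makes sense only if undetectable patients fall below it; as written they are grouped with the patients who were not reversed.

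In the three pooled models, a value of 0 therefore means either a direct-inhibitor patient who stayed at or above 30 ng/mL or any enoxaparin patient. No model has a term for inhibitor, so the odds ratio, likelihood ratio test and ROC area all mix the two. Model 1 is the first model listed for the study's only secondary objective. SAP 5.17.2 says this version was written partly to pre-specify these correlations, and SAP 1.0 describes the 477 patients as locked. A programmer must either run a coding that works against the section's purpose or depart from the SAP without instruction.

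**Working it through.** The plan states no figure to reproduce here. The defect is a matter of logic; only its size needs assumptions.

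**1. Coding as written (5.5.1, 4.3, 5.14, 5.16.3)**

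- Stored value: x′ = max(x, 0.10).
- Nadir = min(x′ at end of bolus, x′ at end of infusion) ≥ 0.10.
- Indicator = 1 if nadir < 0.10, which never occurs.

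On a grid of raw enoxaparin values from 0 to 2.000 IU/mL in steps of 0.001 (2001 values, 100 of them below 0.10), the number coded 1 is:

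| Rule | Coded 1 |
|---|---|
| As written | 0 |
| Below-0.10 flag from the unreplaced result | 100 |
| ≤0.10 after replacement | 101 (adds a measured 0.10) |

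All 196 combinations tried of baseline, end-of-bolus and end-of-infusion values, missing ones included, also give 0. Carrying baseline forward does not help: the Efficacy Population needs at least 0.25 IU/mL, and a safety-population baseline is floored too. The direct-inhibitor rule works: on a grid of 0 to 1200 ng/mL in steps of 0.1, 300 values are coded below 30 and 300 raw values are below 30.

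In an enoxaparin-only model the covariate is constant. The design matrix (intercept plus indicator) has rank 1 of 2, so the odds ratio cannot be estimated.

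**2. Inputs for size**

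- From the documents: 477 patients (SAP 1.0); 30% below the activity threshold and 5% non-evaluable (SAP 3.2), so Model 1 N ≈ 477 × 0.65 = 310; at least 110 evaluable ICH patients; an aim of at most 20% on indirect inhibitors (Protocol 3.1).
- Assumed: enoxaparin share s = 5–20%; fraction of direct-inhibitor patients below threshold b = 0.60; direct-inhibitor success p = 0.75; enoxaparin success e = 0.60–0.90; fraction of enoxaparin patients truly below 0.10, t = 10–90%.

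Miscoded patients in Model 1 = N·s·t: 310 × 0.05 × (0.1 to 0.9) ≈ 2 to 14, and 310 × 0.20 × (0.1 to 0.9) ≈ 6 to 56.

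**3. Model 1 with no true association**

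As written, the below group contains only direct-inhibitor patients, with odds 0.75/0.25 = 3. Success in the reference group is

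r = [(1−s)(1−b)p + s·e] / [(1−s)(1−b) + s].

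At s = 0.20:

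- e = 0.60: r = (0.24 + 0.12)/0.52 = 0.692, odds 2.25, OR = 3/2.25 = 1.33.
- e = 0.90: r = (0.24 + 0.18)/0.52 = 0.808, odds 4.2, OR = 3/4.2 = 0.71.

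Coded correctly, a fraction t of enoxaparin patients moves to the below group:

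r₁ = [(1−s)b·p + s·t·e] / [(1−s)b + s·t], r₀ = [(1−s)(1−b)p + s(1−t)e] / [(1−s)(1−b) + s(1−t)].

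| Share | As written | t = 10% | t = 30% | t = 50% | t = 90% |
|---|---|---|---|---|---|
| 5% | 0.91–1.10 | 0.92–1.08 | 0.95–1.05 | 0.98–1.02 | 0.95–1.05 |
| 20% | 0.71–1.33 | 0.76–1.27 | 0.84–1.15 | 0.94–1.05 | 0.85–1.20 |

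At a 10% share the as-written range is 0.83–1.18. Correct coding gives exactly 1.00 when t equals b (60%). Expected Model 4 odds ratios are the same if its volume and infratentorial covariates are ignored.

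**4. Model 1 with a true odds ratio of 2.0**

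Hold overall success at 75% in both inhibitor types. Solving 0.6p₁ + 0.4p₀ = 0.75 with OR = 2 gives p₀ = 0.671 and p₁ = 0.803 for the direct inhibitors. As written, the estimate is 1.92 at a 5% share and 1.74 at 20%. Coded correctly at 20%, it is 1.81, 1.99 and 1.90 for t = 10%, 50% and 90%.

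**5. Mortality model**

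Take direct-inhibitor mortality of 15%, enoxaparin mortality of 10–25%, no true association, age ignored and a 20% share. As written the range is 0.76–1.17. Coded correctly it is 0.80–1.14, 0.95–1.03 and 0.92–1.17 for t = 10%, 50% and 90%.

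**6. Sampling error for a null odds ratio**

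Var(ln OR) = 1/[N·b·p(1−p)] + 1/[N(1−b)·p(1−p)].

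- Model 1, N = 310: 1/34.875 + 1/23.25 = 0.0717, SE 0.268, limits 0.59–1.69.
- Model 4, N = 110: limits 0.41–2.41.
- Mortality, N = 477, p = 0.15: limits 0.60–1.67.

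**The case against.** The strongest reply is that little depends on this. SAP 5.7 treats secondary analyses as exploratory, the mortality model is a safety analysis, and every null shift above lies inside sampling error. The 20% share is a ceiling for all indirect inhibitors, not an expectation; at 5% a true odds ratio of 2.0 falls only to 1.92. All of this stands and limits the weight of the point.

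Second, part of the distortion comes from pooling inhibitors rather than from the coding. At a 20% share with 10% truly below, correct coding narrows the null range only from 0.71–1.33 to 0.76–1.27. That also stands. It is a reason to add enoxaparin-excluded runs, not a reason to leave the rule alone.

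Third, the SAP admits that no equivalent enoxaparin threshold exists, and Model 2 gives a clean direct-inhibitor counterpart to Model 1. But a stand-in cut-off that no patient can cross does not do the job the SAP gives it. For mortality, SAP 5.16 yields single-inhibitor results. For Model 4, SAP 5.13 may do so, and the sample table list has ICH tables for apixaban and rivaroxaban (14.2.3.2a, 14.2.3.2b, 14.2.3.5). Those tables omit edoxaban and do not say that they use this indicator. No pooled direct-inhibitor version of Model 4 or of the mortality model is specified.

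Finally, SAP 5.9 concerns plasma concentrations and is not shown to reach enoxaparin activity. The conclusion does not need it, since 5.5.1 is enough and 5.5.4 points the same way.

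**Conclusion.** The concern holds. That every enoxaparin patient is coded 0 in Model 1, Model 4 and the mortality model follows from the written rules without any assumption; nothing in the SAP directs the programmer to the unreplaced result. The consequence is uncertain and probably modest. It depends on the enoxaparin share and on the fraction truly below 0.10 IU/mL, neither of which is in the documents, and the odds ratios above are illustrations on assumed rates.

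No primary claim is touched, and Models 2 and 3 and the direct-inhibitor part of the indicator are sound. It should be fixed because the rule contradicts its own section's purpose, leaves the enoxaparin-only odds ratio inestimable and is cheap to correct. Correct coding removes most of the distortion only if the truly-below fraction for enoxaparin is close to that for the direct inhibitors.

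**What to change.** 1. In SAP 5.14 and 5.16.3, for enoxaparin only, derive the indicator from the laboratory result reported as below 0.10 IU/mL, before the detection-limit replacement in 5.5.1. If that flag was not kept, use ≤0.10 after replacement for enoxaparin only, and state that a measured 0.10 then also counts.
2. State that this bypasses only the detection-limit replacement, and say how a nadir carried forward from baseline is coded. This matters in the safety population, where baseline itself may be below 0.10.
3. Leave the 30 ng/mL rule and the 5.5.1 replacement for the percent-change endpoint unchanged. SAP 4.5.5 shows a replacement that avoids the problem (anti-factor IIa below 0.04 becomes 0.02), but using that approach here would alter the percent-change endpoint.
4. Report the number of enoxaparin patients in each indicator cell.
5. Add pooled direct-inhibitor (enoxaparin-excluded) runs of Model 4 and of the mortality model, as Model 2 does for Model 1.

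The cost is one derivation line in two SAP sections, a short note on carried-forward nadirs, a cell count and two extra model runs on data already collected.
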